4.0 Study Endpoints (if applicable)

Primary outcome variables include:

- Evidence-based cessation treatment utilization will be assessed via participant self-report. At each follow-up assessment, participants in both groups will be queried for: 1) use of a smoking cessation medication since the last assessment, 2) how the medication was obtained (e.g., via the study or another outlet such as MUSC's existing smoking cessation service), and 3) receipt of the 5As from their PCP⁶.
- Cessation-related outcomes will be assessed via participant self-report. Cigarette smoking, use of other tobacco products (e.g., e-cigarettes), and quit attempts/quit duration will be assessed at each follow-up using a timeline followback for the last 6-months at baseline and since prior follow-up for each subsequent assessment^{7,8}.
- COPD diagnosis will be assessed both via established metrics captured via home spirometry and via chart review.

Secondary outcome variables include:

- E-visit acceptability and feasibility will be assessed both by examining the percentage of patients who complete the initial and follow-up e-visits, and by participant self-report during follow-up assessments. Participants will respond to items assessing ease of use, satisfaction, and pros/cons of the e-visit. Analytics data (e.g., amount of time it takes to complete the e-visit, amount of time it takes the provider to review the e-visit) will also be collected as will data on provider fidelity to e-visit recommendations (captured by reviewing within Epic whether the provider administered treatment consistent with e-visit recommendations).

We will also assess:

- Nicotine dependence will be assessed at baseline via the Fagerstrom Test of Nicotine Dependence⁹.
- Motivation to quit and confidence in quitting will be assessed via participant self-report using a modified Contemplation Ladder¹⁰.

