11.0 Data Analysis and Data Management

Data Analysis

As this is a pilot trial, our primary goal is to estimate an intervention effect size and our secondary goal is to examine the feasibility/acceptability of the e-visit. Precise parameter estimation can be achieved with 25-30 participants per group¹². To estimate an effect size for the smoking cessation e-visit intervention, we will randomize participants 2:1 (active:control), with 67 participants in the active condition and 33 in the control condition. Primary smoking-related outcomes for this trial include cessation treatment utilization (e.g., medication) and quit attempts. Assuming a cessation treatment utilization rate of 48% in the active condition and 11% in the control condition, with 2:1 randomization we will have 95% power to detect an effect. For quit attempts, assuming a quit attempt rate of 24% in the e-visit condition and 6% in the TAU condition, we will have 60% power to detect an effect. Our intent here is not a fully powered trial for cessation, but is rather to collect preliminary data to inform future trials.

Data analysis for the primary objective will focus on descriptive analysis of primary smoking-related outcomes. Descriptive statistics (e.g., frequencies, percentages) will be calculated for the primary smoking-related outcomes (treatment utilization, quit attempts). Because rates of these primary outcomes are expected to be low in control group, we will utilize Fisher's exact tests to compare rates between the e-visit and TAU groups. Secondary exploratory analyses for this primary objective will examine changes in these outcomes over time by treatment condition. We will utilize Generalized Estimating Equations (GEEs) with log link functions, which will allow us to account for correlated repeated measures within study participants. Planned covariates include sex and the main effect of time.

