This section is based on the recommendations in NIDA's "Guidelines for developing a Data and Safety Monitoring Plan" as well as NCI's "Essential Elements of a Data and Safety Monitoring Plan for Clinical Trials Funded by the National Cancer Institute."

Summary of the Protocol

We will develop and iteratively test a comprehensive e-visit for delivery to smokers treated via primary care. Through an established partnership with MUSC Epic developers, we will develop the e-visit consistent with USPHS best practice guidelines for smoking cessation treatment via primary care. Those who self-report symptoms of COPD will be invited to complete home spirometry. We will then complete a randomized pilot trial of 1) e-visit vs. 2) TAU.

Trial Management

The study will be managed from the Addiction Sciences Division within the Department of Psychiatry and Behavioral Sciences at the Medical University of South Carolina (MUSC). Recruitment, data collection, data management, and treatment provision will be coordinated and centrally managed at our research lab at MUSC and will be implemented within local MUSC clinics.

Data Management and Analysis

Participants will enter data in REDCap, a secure, web-based application designed exclusively to support data capture for research studies. REDCap provides: 1) an intuitive interface for data entry (with data validation); 2) audit trails for tracking data manipulation and export procedures; 3) automated export procedures for seamless data downloads to common statistical packages (SPSS, SAS, Stata, R); 4) procedures for importing data from external sources; and 5) advanced features, such as branching logic and calculated fields. These procedures are effective in minimizing data entry errors (e.g., missing or errant data). The data analysis plan is outlined above.

Quality Assurance

Accuracy and completeness of the data collected will be ensured by weekly review. The REDCap system does not accept outliers, illogical response patterns, etc. The PI and research assistants will have weekly meetings to discuss any qualitative comments received during data collection and any problems in data collection. The PI will examine the database for potential irregularities monthly. Initial data analyses will examine distributions of variable scores and comparability of baseline characteristics across conditions in case analyses need to be adjusted for these. Confidentiality procedures are outlined above.

Regulatory Issues

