All screening information will be kept in a password protected REDCap database. Only key study personnel will have access to the database. If an individual is not eligible to participate, his/her screener will include his/her first name and last initial and the reason for disqualification. Eligible participants' full name, telephone number and e-mail address will be recorded in the database. This is the only place where participants' names and subject identification numbers appear together. Eligible participants will be assigned a subject number, will complete informed consent, will be randomized, will complete baseline assessments, and subsequently will receive their randomized intervention.

Upon completing eligibility screening, if study eligible, individuals will be provided with an overview of the study, asked to review study procedures via a consent form, and asked to provide signed consent. Participants will be informed of limitations of confidentiality (i.e., abuse or neglect, intention to harm self or someone else) both verbally and/or in writing during the informed consent process. The consent form will include the participant's name, but not his/her subject number. Consent forms will be provided in English. As utilization of the smoking cessation e-visit requires that participants are able to read, participants unable to read the consent form on their own will not be included.

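### Covariates beyond sex and time in the exploratory GEE would be picked by chance baseline imbalance, while collected, plausibly prognostic baseline values are not planned covariates

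*Combined protocol and SAP*

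**What the plan says.** The main between-arm analysis is in Section 11.0 (Data Analysis). Treatment utilization and quit attempts are summarised as frequencies and percentages, and "we will utilize Fisher's exact tests to compare rates between the e-visit and TAU groups". No covariates enter.

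A model follows at a lower level: "Secondary exploratory analyses for this primary objective will examine changes in these outcomes over time by treatment condition". Its form is given as "We will utilize Generalized Estimating Equations (GEEs) with log link functions", and "Planned covariates include sex and the main effect of time".

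A separate sentence in Section 12.0 (Quality Assurance) says that initial analyses will examine "comparability of baseline characteristics across conditions in case analyses need to be adjusted for these". It gives no list of variables, no criterion for imbalance, and no indication of which analysis would be adjusted.

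Section 4.0 lists baseline information that is not among the planned covariates. "Nicotine dependence will be assessed at baseline via the Fagerstrom Test of Nicotine Dependence", and a timeline followback at baseline covers smoking and quit attempts over the previous six months. Also, "Motivation to quit and confidence in quitting will be assessed via participant self-report using a modified Contemplation Ladder", with no time point stated.

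On order, Section 13.0 (Protections Against Risk) says that eligible participants, after consent, "will be randomized, will complete baseline assessments", and then receive the intervention.

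**The concern.** In a randomised comparison with baseline recorded before the arm is known, differences between arms at baseline are chance. The reason to adjust is that a covariate predicts the outcome. Imbalance alone is a poor criterion: it can bring in variables that do not matter and leave out ones that do.

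With no variables, criterion or target analysis stated, two analysts following the text could report different adjusted estimates from the same data. This matters because Sections 1.0 and 11.0 make an effect size for a larger trial the primary goal. The pilot is small and outcomes are few, so an adjusted estimate can move appreciably with the choice of covariate. The precision available from baseline data already being collected would also go largely unused.

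**Working it through.** **Inputs from Section 11.0.** 67 active and 33 control; quit attempts 24% against 6%, stated power 60%; treatment utilization 48% against 11%, stated power 95%. Alpha and sidedness are not stated; 0.05 two-sided is assumed.

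**1. The plan's own figures.** Exact enumeration of Fisher's test at 67:33 gives 60.1% power for quit attempts, which reproduces the stated 60%. For utilization, Fisher's test gives 97.7% and a continuity-corrected normal approximation 96.4%, so the stated 95% is slightly conservative. The stated power is thus consistent with the unadjusted test, and nothing in this point disputes it.

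**2. How many covariates the data can carry.**
- Quit attempts: 0.24 × 67 = 16.1 and 0.06 × 33 = 2.0, about 18 participants in all.
- Utilization: 0.48 × 67 = 32.2 and 0.11 × 33 = 3.6, about 36 in all.

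With about 2 events expected under TAU for quit attempts, one covariate beyond sex and time is the most that is sensible.

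**3. How often a trigger might fire by chance.** The plan gives neither a cut-off nor a number of variables. If k independent variables were each tested at 0.05, the chance of at least one flag under proper randomisation is 1 − 0.95^k:
- k = 5: 1 − 0.774 = 0.23
- k = 10: 1 − 0.599 = 0.40
- k = 15: 1 − 0.463 = 0.54

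This shows only how often adjustment might be prompted. Correlated variables would change the figures.

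**4. What the trigger does to power and error (illustration).** The simulation used 4,000 runs, 67:33, five independent normal baseline variables of which two are prognostic, and a logistic model at one time point, with a 20% control rate at the covariate mean and a treatment log-odds of 1.2. The trigger was p < 0.05 on a t-test. All of this except the 67:33 split is assumed.

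| Prognostic strength (log-odds per SD) | Power, unadjusted | Power, triggered | Power, prespecified |
|---|---|---|---|
| 0 | 72.0% | 71.8% | 72.5% |
| 0.5 | 63.0% | 63.2% | 68.3% |
| 0.8 | 55.2% | 55.7% | 65.4% |

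Type I error was 3.7% to 3.9% with the trigger and 4.0% to 5.0% with prespecified adjustment. The prespecified model here used both prognostic variables; a single covariate would be expected to gain less.

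**5. How far the estimate can move (illustration).** Using the plan's quit-attempt rates, a logistic model and one covariate imbalanced at p < 0.05, adjustment changed the treatment odds ratio by a median factor of about 1.25 (0.5 per SD) or 1.40 (0.8 per SD). For utilization at 0.5 per SD the factor was about 1.20. Part of this shift arises because odds ratios change on adjustment even in balanced data. The plan's log link, which yields rate ratios, would not share that part.

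**The case against.** The strongest reply is that this is one contingent sentence in a quality-assurance paragraph. That paragraph itself refers the reader back to Section 11.0 for the analysis plan, where sex and time are already fixed. The main comparison is unadjusted and the GEE is labelled exploratory, so an unadjusted estimate will exist whatever the balance check shows. All of that stands, and it limits the point to additional covariates in a secondary model.

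A reader might infer more, and the documents do not support it:
- **That the primary result depends on the balance check.** Fisher's test takes no covariates.
- **That the whole covariate set is data-driven.** Sex and time are named in advance.
- **That type I error is inflated or intervals are invalid.** Simulated type I error stayed below 5% under the trigger. Coverage was not examined, and Section 11.0 specifies no intervals.
- **That 40%, or any figure from 23% to 54%, measures harm.** The plan describes no significance testing of baseline variables, so these figures rest on an assumed procedure.

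It is also fair to say that the documents nowhere call nicotine dependence or quit history prognostic. The gain from adjustment all but disappears if they are not. A short covariate list is defensible with so few events.

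Finally, nicotine dependence comes from the same baseline assessment that Section 13.0 lists after randomisation. That section does not say that participants know their arm by then, but it does not rule it out. The remedy therefore has to include the timing of whichever covariate is chosen.

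**Conclusion.** The point holds as a modest improvement, not as an error that threatens the main comparison. Balance-triggered adjustment leaves the exploratory adjusted estimate undefined until the data are seen. In the illustration it bought almost no precision: 0.2 percentage points of power at moderate prognostic strength, against 5.3 points for prespecified adjustment, and 0.5 against 10.2 points at strong prognosis.

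Those sizes rest on assumed prognostic strength, a 0.05 trigger, five independent variables and a one-time-point logistic model in place of the planned repeated-measures log-link GEE. The argument that covariates should be fixed in advance for their prognostic value does not depend on the particular figures. The choice of nicotine dependence is a subject-matter assumption. Baseline quit attempts are an alternative, but they might instead enter the GEE as a repeated time point, and the text does not say.

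**What to change.** - **Section 12.0:** delete the clause that makes adjustment depend on baseline comparability. Say instead that baseline characteristics will be shown by arm descriptively, without tests.
- **Section 11.0:** keep Fisher's test unadjusted. State that the GEE covariates are sex, time and one named baseline value, for example nicotine dependence, used whatever the observed balance and reported beside the unadjusted estimate. Label any further adjustment as a sensitivity analysis.
- **Timing:** state that the chosen covariate is recorded before the participant learns the assignment. Do not adjust for motivation or confidence unless the same holds for them.

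The cost is about one sentence in each of Sections 11.0 and 12.0, plus a check on the order of baseline assessment and disclosure of the arm. No extra participants or measures are needed. The downside is less freedom to add covariates later. The single added covariate must be chosen with care, because about 18 expected quit attempters, roughly 2 of them under TAU, will not support more.

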13.0 Risks to Subjects

This is considered a minimal risk study. Minimal risk means the probability and magnitude of harm or discomfort anticipated in the research are not greater in and of themselves other than those ordinarily encountered in daily life or during performance of routine physical or psychological examinations or tests. The potential risks in this study include those related to: a) smoking cessation medications, b) confidentiality, and c) frustration.

a) Smoking cessation medications: Participants in both treatment arms may receive an FDA-approved smoking cessation medication. Participants in the e-visit condition may receive a prescription as an outcome of the e-visit and participants in the TAU condition may receive a prescription if they contact their PCP to discuss quitting smoking. These medications include: nicotine replacement therapy (NRT), varenicline, and/or bupropion. Participants will be educated about their smoking cessation medication as part of the e-visit or during their normally scheduled medical appointment if randomized to the TAU condition. Pregnancy or intention to become pregnant will be assessed during the e-visit. Medication will only be prescribed if a participant does not have contraindications for that medication. Participants will be provided with our study phone number and instructed to call our study personnel should they experience AEs or if they have questions/concerns about medication use. Given the relatively benign risk profiles of these medications, we expect AEs, which will be assessed across follow-up timepoints via REDCap, to be rare and mild. Participants will be encouraged to contact [name] as soon as possible for serious AEs and for those conditions that labeling suggests seeing a provider. We will withdraw participants who have a serious AE. For other AEs, if the participant wishes it, the participant will be withdrawn from the study.

b) Confidentiality: Participants will be made aware of limits to confidentiality at the beginning of screening and when reviewing study procedures/during informed consent which include report of suicidal or homicidal intent or report of abuse or neglect. If the participant reports suicidal or homicidal intent or abuse/neglect, [name] will take appropriate action as outlined by the MUSC IRB, NIH, and the State of South Carolina, which may include contacting the authorities and/or pursuing involuntary commitment at a mental health facility. If participants present no imminent danger but also need more extensive treatment of mental health concerns, they will be given appropriate referrals and instructed to contact their physician.

c) Frustration: Participants may become frustrated while completing study assessments. Participants will be informed that they may refuse to answer any question(s) that they do not wish to answer and that they may discontinue study participation at any time.

Since patients will all currently be receiving medical care at MUSC, there are no additional risks associated with participation in this study.

Adequacy of Protection Against Risks

Recruitment and Informed Consent

Study participants will be recruited from local MUSC clinics. Smoking status is assessed for every patient, consistent with MUSC's best practice guidelines. Patients identified as smokers via the EMR will be sent a message inviting them to participate in a research study. Interested patients will complete determination of eligibility via MUSC's REDCap system, a secure, HIPAA-compliant data management system. All participants will review consent documents and will provide informed consent consistent with procedures outlined above. Participants will be given the opportunity to ask questions about their participation throughout the course of the study. A copy of the informed consent will be kept centrally at our study office

within locked filing cabinets, and a copy will be given to each study participant as well. Participants will be given a study phone number and e-mail address to contact for questions.

Protections Against Risk

All screening information will be kept in a password protected REDCap database. Only key study personnel will have access to the database. If an individual is not eligible to participate, his/her screener will include his/her first name and last initial and the reason for disqualification. Eligible participants' full name, telephone number and e-mail address will be recorded in the database. This is the only place where participants' names and subject identification numbers appear together. Eligible participants will be assigned a subject number, will complete informed consent, will be randomized, will complete baseline assessments, and subsequently will receive their randomized intervention.

Upon completing eligibility screening, if study eligible, individuals will be provided with an overview of the study, asked to review study procedures via a consent form, and asked to provide signed consent. Participants will be informed of limitations of confidentiality (i.e., abuse or neglect, intention to harm self or someone else) both verbally and/or in writing during the informed consent process. The consent form will include the participant's name, but not his/her subject number. Consent forms will be provided in English. As utilization of the smoking cessation e-visit requires that participants are able to read, participants unable to read the consent form on their own will not be included.

Regarding questionnaire data, data will be obtained for research purposes only. All data will be collected, stored, and managed via REDCap, which is a secure, web-based application designed exclusively to support data capture for research studies. REDCap provides secure, web-based flexible applications, including real time validation rules with automated data type and range checks at the time of entry. The underlying database is hosted in a secure data center at MUSC, a secure environment for data systems and servers on campus, and includes redundancy, failover capability, backups and extensive security checks. The system has several layers of protection including user/group account management, "Data Access Groups" which allow data to be entered by multiple groups in one database with segmented user rights for entered data, audit trails for all changes, queries and reports, and Secure Sockets Layer (SSL) encryption. Name and relevant contact information will be obtained to provide compensation and every effort will be made to maintain subject confidentiality, in accordance with HIPAA. All data will be identified only by code numbers (participant IDs). Participant IDs will be linked to participants' names in a password-protected file that is accessible only to the PI and trained research staff.

Protection against risks associated with smoking cessation medications include a Data and Safety Monitoring Plan that includes monitoring of AEs. FDA contraindications for each smoking cessation medication will be factored into the smoking cessation e-visit. Through informational material provided via the e-visit and with standard medication packaging, participants will be educated about potential AEs and nicotine intoxication symptoms (for NRT medications). We anticipate very few AEs. AE's will be discussed with Drs. [name] and/or [name].

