A two-arm pilot RCT (N=100, up to 120 assuming 20% attrition) will test cessation treatment utilization, smoking cessation outcomes, and COPD diagnosis rates as a function of smoking cessation e-visit vs. TAU. Recruitment will primarily occur proactively and remotely via the EMR. We will conduct an automated EMR search via established procedures for all patients treated within MUSC DFM clinics during the past 12 months who: 1) smoke, 2) are ≥ 40 , 3) have MyChart accounts, and 4) do not have COPD on their problem list. **These patients will be sent a MyChart message from a member of their care team inviting them to participate in a research study for cigarette smokers. These messages will only be sent to patients of PCPs who have agreed that their patients may be contacted for the purpose of this study. This invitation will include clear opt out procedures should the patient not wish to be contacted in the future for the purpose of this study. Clinical providers included in the Usability Testing phase of the project will not be asked to directly refer their own patients to the study. However, their patients may still be recruited via the EMR.** After sending these automated e-mail messages via MyChart, the study team may also call, e-mail, and/or text message potential participants to notify them that a message was sent to them via MyChart. Again, such contact will only be made to patients of PCPs who have agreed that their patients may be contacted for the purpose of this study. If interested, participants will complete a screening online via MyChart to determine study eligibility (see above for inclusion criteria). After completing determination of eligibility, if eligible and interested in participating in the study, participants will be scheduled for a time to complete informed consent (see 9.0 Consent Process). After consent is obtained, participants will be randomized 2:1 to receive either the smoking cessation e-visit or TAU. If randomized to the e-visit condition, participants will be sent a link to initiate the e-visit. All e-visit medication recommendations will be reviewed by physicians included on this IRB protocol. Medications will be e-prescribed to a mail order pharmacy (e.g., MUSC's mail order pharmacy) and then mailed to participants, with all costs covered by the study. Note

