All participants will subsequently be text messaged and/or emailed a REDCap link, accessible via smartphone, tablet, or computer to complete study assessments. These assessments will occur at baseline (following consent), 1-month following study enrollment, and 3-months following study enrollment. Assessments are estimated at 20 minutes each and will be administered remotely via REDCap through our established procedures. Participants will be compensated via electronic gift cards (e.g., Amazon) which will be emailed or texted to participants. Participants will receive \$30 for completion of the baseline assessment questionnaire. After completing each follow-up questionnaire within 72 hours of being emailed the link, participants will be compensated \$30. Participants will be compensated \$30 for each completed carbon monoxide recording. They will be compensated an additional \$100 for completion of all three sets of questionnaires and both carbon monoxide samples. E-visit acceptability and feasibility will be assessed both by examining the percentage of patients who complete the initial and follow-up e-visits, and by participant self-report during follow-up assessments. Participants will respond to items assessing ease of use, satisfaction, and pros/cons of the e-visit. Analytics data (e.g., amount of time it takes to complete the e-visit, amount of time it takes the provider to review the e-visit) will also be collected as will data on provider fidelity to e-visit recommendations (captured by reviewing within Epic

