whether the provider administered treatment consistent with e-visit recommendations). Cigarette smoking, use of other tobacco products (e.g., e-cigarettes), and quit attempts/quit duration will be assessed at each follow-up using a timeline followback for the last 6-months at baseline and since prior follow-up for each subsequent assessment^{7,8}. Nicotine dependence will be assessed at baseline via the Fagerstrom Test of Nicotine Dependence⁹. Participants will report motivation to quit and confidence in quitting using a modified Contemplation Ladder¹⁰. Expired air carbon monoxide will also be captured. Treatment utilization will be assessed via participant self-report. At each follow-up assessment, participants in both groups will be queried for: 1) use of a smoking cessation medication since the last assessment, 2) how the medication was obtained (e.g., via the study or another outlet such as MUSC's existing smoking cessation service), and 3) receipt of the 5As from their PCP⁶. COPD diagnosis will be assessed via participant self-report and via medical records review. At each follow-up time point, participants will be asked whether a clinical provider has given them a COPD diagnosis. Medical records will be reviewed for up to 12-months following completion of the 3-month follow-up survey to identify: 1) whether the participant was referred for in person spirometry, 2) whether the participant attended that appointment, and 3) whether the participant was given a diagnosis of COPD.

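### The serious-AE rule in section 13.0 reads as withdrawal from the study, so a few randomised participants could lose later outcomes, possibly selectively for COPD diagnosis

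*Combined protocol and SAP*

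**What the plan says.** Section 13.0, item (a) on smoking cessation medications, gives the rule: "We will withdraw participants who have a serious AE". It then adds: "For other AEs, if the participant wishes it, the participant will be withdrawn from the study". The first sentence is mandatory. The second depends on the participant's wish, and it is the one that names what the participant is withdrawn from.

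The same item describes how AEs are found, "which will be assessed across follow-up timepoints via REDCap", and asks participants to get in touch promptly if a serious AE occurs.

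On outcomes, section 4.0 lists COPD diagnosis among the primary outcome variables: "COPD diagnosis will be assessed both via established metrics captured via home spirometry and via chart review". Section 10.0 sets the schedule ("These assessments will occur at baseline (following consent), 1-month following study enrollment, and 3-months following study enrollment") and adds two further sources for COPD. At each follow-up, "participants will be asked whether a clinical provider has given them a COPD diagnosis". In addition, "Medical records will be reviewed for up to 12-months following completion of the 3-month follow-up survey", to find spirometry referral, attendance and COPD diagnosis.

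Section 12.0 requires serious AEs and their follow-up to be reported, and AEs that cause dropout to be recorded. Section 11.0 has no rule for missing outcomes and no statement that participants are analysed in their randomised group.

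**The concern.** A rule that ends participation because of a clinical event produces missing data for a reason that may be related to the outcome. Here the exposed outcome is COPD diagnosis. The participants are smokers aged 40 or over without COPD on their problem list. A serious respiratory event in such a person could trigger withdrawal and could also lead to the diagnosis that the trial wants to count. Those removed may then be more likely than average to have the outcome.

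The trial's stated purpose is to supply effect-size estimates for a larger RCT, so selective loss of even a few diagnoses would weaken that estimate, and the wording could be carried into the larger protocol. No comparable mechanism is claimed for treatment utilization or quit attempts, the two outcomes to be compared by Fisher's exact test.

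**Working it through.** **1. Which outcomes are at risk.** Only outcomes collected after the event can be lost.

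| Serious AE becomes known | Survey outcomes lost under study withdrawal |
|---|---|
| Before the 1-month assessment | 1-month and 3-month |
| At the 1-month assessment | 3-month only |
| At the 3-month assessment | None; only chart review is in question |

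**2. How many people.** The documents give no serious-AE rate. The 5% ceiling in section 12.0 is for significant AEs, which the same section lists separately from serious ones. I therefore assume 1% to 5%.

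- All enrolled: 0.01 × 120 = 1.2 and 0.05 × 120 = 6, so about 1 to 6.
- By arm at 2:1 (80 e-visit, 40 TAU): 0.8 to 4 in e-visit and 0.4 to 2 in TAU, so about 1 to 4 and 0 to 2.

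This is an upper count, because step 1 shows that not everyone affected loses every outcome.

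**3. Ceiling on bias in one arm.** Suppose k of n participants are lost. Let q be the event rate among those kept and l the rate among those lost. The full rate is p = [(n − k)q + kl]/n, so p − q = (k/n)(l − q), and |p − q| ≤ k/n.

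- E-visit: 1/80 = 1.25 points, up to 4/80 = 5 points.
- TAU: 0 up to 2/40 = 5 points.

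These are mathematical ceilings for a complete-case rate, reached only if the lost and kept participants differ completely. Loss in the same direction in both arms partly cancels in the difference. The actual bias in COPD diagnosis cannot be sized, because the plan gives no expected rate.

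**4. Power.** I reproduced the plan's figures first. I used two-sided Fisher exact power at alpha 0.05 by full enumeration; section 11.0 states neither alpha nor sidedness.

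| E-visit/TAU | Treatment utilization, 48% vs 11% | Quit attempts, 24% vs 6% |
|---|---|---|
| Plan states (67/33) | 95% | 60% |
| Recomputed, 67/33 | 97.7% | 60.1% |
| 120 enrolled, 6 lost (76/38) | 98.9% | 66.8% |
| 100 enrolled, 5 lost (64/31) | 96.3% | 57.6% |

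The quit-attempt figure reproduces. The utilization figure is slightly conservative. Losing only these six from 120 leaves more power than planned, and taking five out of 100 costs 2.5 points at most.

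**5. Scale.** The 95% half-width for the quit-attempt difference at 67/33 is 1.96 × √(0.24 × 0.76/67 + 0.06 × 0.94/33) = 0.1305, or 13.0 points. Sampling error on an outcome of that kind is well above the 5-point ceiling for either arm.

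**6. Chart review.** The items sought include referral for in-person spirometry and attendance. Sections 3.0 and 10.0 place that referral after the baseline e-visit, and the study pays only for tests done by the 3-month assessment. The review must therefore cover the period before the 3-month survey, so the 12-month wording is best read as setting an end date. That end date is undefined for anyone who does not complete the survey, whether withdrawn for a serious AE or missing for another reason.

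**The case against.** The strongest reply has five parts.

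- **Scope.** The sentence sits under medication risks, among remarks on contraindications and labelling. A rule limited to medication-related events, or to stopping medication, is plausible. This stands as a statement of possible intent, but no such limit is written, and staff would apply the sentence as it reads.
- **Chart review.** A reader might infer that a withdrawn participant's chart-based COPD outcome is necessarily lost, because the review is dated from a survey that the participant never completes. The documents do not support this. Review needs no contact, is not said to stop on withdrawal, and must reach back before that survey. A COPD diagnosis made during the serious event could also already be in the record. This part stands.
- **Consequence.** A reader might infer a demonstrated bias in the COPD comparison, or a loss of power. Neither is shown. Bias of any size would need a respiratory event, full study withdrawal, an end to chart review, and a diagnosis not yet recorded. Section 11.0 plans no test or power for COPD diagnosis.
- **Safeguards.** Section 12.0 records AEs that cause dropout and reports retention and disposition. The loss would be visible, although not recovered.
- **Consent terms.** The consent form is outside the reviewed text and may cover use of data after withdrawal. This also stands.

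These replies reduce the severity. They do not remove the gap for the 1- and 3-month assessments, which need the participant to stay in the study.

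**Conclusion.** The point holds as a minor one. As written, the rule most naturally removes participants with a serious AE from the study, and nothing in the reviewed text keeps them in the 1- and 3-month assessments. On an assumed 1% to 5% serious-AE rate, about 1 to 6 of 120 would lose one or both later surveys, including self-reported COPD diagnosis. Loss of chart-review data is possible but uncertain. The loss may be selective for COPD diagnosis, by an amount that cannot be estimated from the documents. Confidence is medium, because the conclusion depends on reading the rule as study withdrawal and on consent terms that were not available.

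**What to change.** Replace the sentence in section 13.0 with a rule that separates treatment from data collection:

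- After a serious AE, the study physicians decide whether study medication stops.
- The 1- and 3-month assessments, AE follow-up and chart review continue unless the participant withdraws consent for data collection.
- The chart-review end date is counted from the scheduled 3-month date, not from completion of the survey. This also gives an end date for anyone who misses that survey for another reason.
- These participants are analysed in their randomised group.

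The cost is a short amendment and a few contacts that are already scheduled. It needs no extra participants or procedures, and safety reporting is unchanged.
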